Appendix 6. Optional Intensive Pharmacokinetic Sub-study Recommended Meal Examples

CCI

Appendix 7. Child-Pugh-Turcotte Score {Pugh 1973}

Parameter	Points Assigned		
	1	2	3
Albumin	> 3.5 g/dL (35 g/liter)	2.8 - 3.5 g/dL (28 to 35 g/liter)	< 2.8 g/dL (< 28 g/liter)
Ascites	Absent	Slight	Moderate to Severe
Bilirubin	< 2 mg/dL (< 34.2 micromol/liter)	2 - 3 mg/dL (34.2 to 51.3 micromol/liter)	> 3 mg/dL (> 51.3 micromol/liter)
Encephalopathy	None	Grade 1 – 2	Grade 3 - 4
Prothrombin time			
Seconds over control	< 4	4 – 6	> 6
INR	< 1.7	1.7 – 2.3	> 2.3

Modified Child-Pugh-Turcotte classification of the Severity of Liver Disease

	Class A	Class B	Class C
Total Points	5-6	7-9	10-15
Severity of Hepatic Cirrhosis	Well-compensated	Significant Functional Compromise	Decompensated
1- and 2- year survival	100% and 85%	80% and 60%	45% and 35%

1. ASSESSMENT OF COVID-19 IMPACT

This study was ongoing during the novel coronavirus (2019 nCoV [COVID-19]) pandemic, which has caused a disruption in the regular visit schedules for this study. Some study subjects were unable to attend onsite visits due to shelter in place guidelines, site closures, or other reasons. This section provides guidance on handling special situations due to the COVID-19 pandemic in the final analysis.

Adverse events (AEs) attributed as being due to the COVID-19 pandemic will be included in all AE analyses specified in the SAP, if applicable. A by-subject listing of all AEs due to the COVID-19 pandemic will be provided.

1.1. Study Drug or Study Discontinuation Due to the COVID-19 Pandemic

A by-subject listing of reasons for premature study drug or study discontinuation due to the COVID-19 pandemic will be provided.

1.2. Protocol Deviations Due to the COVID-19 Pandemic

By-subject listings will be provided for subjects with important and non-important protocol deviations due to the COVID-19 pandemic, respectively.

1.3. Missed or Virtual Visits Due to the COVID-19 Pandemic

Information regarding missed or virtual visits due to the COVID-19 pandemic will be collected as free text in the CRF comment fields. The determination of missed or virtual visits due to the COVID-19 pandemic will be done using a Natural Language Processing (NLP) algorithm by analyzing the CRF comment fields. A detailed explanation of the algorithm is provided in [Appendix 1](#).

A by-subject listing of subjects with missed or virtual visits due to the COVID-19 pandemic will be provided by subject ID number in ascending order.

2. ANALYSIS WINDOWS FOR WEEK 96

For the final analysis, no upper limit will be applied to the Week 96 analysis window in Table 3-2 to Table 3-8 in the SAP.

3. IMPUTATION FOR LAST DOSE DATE

If the last dose date is completely missing, please refer to the SAP Section 3.8.1 for imputation rules.

If the last dose date is partially missing, the latest of non-missing study drug start dates and end dates, the clinical visit dates, and the laboratory visit dates will be used to impute the last dose date if the imputed month/year is no earlier than the partial last dose month/year (if month/year is not missing).

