In Study GS-US-320-0108, no subject in either treatment group experienced HBsAg loss by Week 48. In Study GS-US-320-0110, 4 subjects (0.7%) in the TAF group and 1 subject (0.3%) in the TDF group experienced HBsAg loss at Week 48. Three of the 4 subjects in the TAF group and none in the TDF group also experienced HBsAg seroconversion at Week 48.

In Study GS-US-320-0110, the proportion of subjects with HBeAg loss or seroconversion to anti-HBe at Week 48 was also evaluated; these data are presented on [Table 1-4](#). A total of 78 (13.8%) and 34 (11.9%) subjects in the TAF and TDF groups, respectively, had HBeAg loss at Week 48. A total of 58 (10.3%) and 23 (8.1%) subjects in the TAF and TDF groups, respectively, experienced HBeAg seroconversion at Week 48.

Table 1-4. GS-US-320-0110: Proportion of Subjects with HBeAg Loss or Seroconversion at Week 48, Missing = Failure (Serologically Evaluable Full Analysis Set)

	GS-US-320-0110			
	TAF 25 mg (N = 565)	TDF 300 mg (N = 285)	TAF 25 mg vs TDF 300 mg	
			p-value	Prop Diff (95% CI)
HBeAg Loss, n (%)	78/565 (13.8%)	34/285 (11.9%)	0.47	1.8% (-3.0% to 6.5%)
HBeAg Seroconversion, n (%)	58/565 (10.3%)	23/285 (8.1%)	0.32	2.1% (-2.0% to 6.3%)

P-values were from the Cochran-Mantel-Haenszel test stratified by baseline HBV DNA categories and oral antiviral treatment status. Differences in the proportion between treatment groups and its 95% CI were calculated based on the Mantel-Haenszel proportions adjusted by baseline HBV DNA categories and oral antiviral treatment status strata.

Serologically Evaluable Full Analysis Set for HBeAg loss/seroconversion included subjects who were HBeAg positive and HBeAb negative/missing at baseline. HBeAg loss was defined as changes from HBeAg-positive at baseline to HBeAg-negative at a post-baseline visit with baseline anti-HBe negative/missing. HBeAg seroconversion was defined as HBeAg loss and anti-HBe change from negative/missing at baseline to positive at a post-baseline visit.

Source: GS-US-320-0110 Week 48 CSR, Section 15.1, Table 19.1

Virologic Resistance Analysis

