Subjects in Part A (renally impaired) with HBsAg loss with confirmed seroconversion to anti-HBs should discontinue study drug within 3-6 months following confirmation of seroconversion to anti-HBs. Subjects with HBsAg loss with confirmed seroconversion prior to Week 24 are not permitted to discontinue study drug prior to the Week 24 visit. Subjects with HBsAg loss with confirmed seroconversion will be followed off treatment every 4 weeks for 12 weeks and then per the study visit schedule ([Appendix 2](#)) through Week 96/Early Discontinuation (ED). Discontinuation of study drug for subjects experiencing HBsAg loss with confirmed seroconversion, who have known bridging fibrosis or compensated cirrhosis, should be considered on a case by case basis.

Subjects with moderate or severe hepatic impairment (Part B) who experience HBsAg loss and seroconversion to anti-HBs should not discontinue study drug.

Subjects in Part A (renally impaired) who permanently discontinue study drug (either prematurely or after completing 96 weeks of treatment) for reasons other than HBsAg loss with confirmed seroconversion to anti-HBs will be followed every 4 weeks for 24 weeks off treatment or until initiation of appropriate, alternative HBV therapy, whichever occurs first. Use of appropriate, alternative HBV therapy is strongly encouraged.

For subjects in Part B (hepatic impairment) who permanently discontinue study drug, immediate initiation of appropriate, alternative HBV therapy is strongly recommended.

A data monitoring committee (DMC) will review the progress of the study and perform review of safety data after 30 subjects have completed 12 weeks of treatment. However, Gilead will defer to the DMC for any decision to convene earlier or more frequently. The DMC will examine the safety results of the trial and also focus on logistical issues such as accrual, retention, quality of clinical and laboratory data, and implications of results of external studies. No formal stopping rules will be used by the DMC for safety outcomes. Rather, a clinical assessment will be made to determine if the nature, frequency, and severity of adverse effects associated with study treatment warrant the early termination of the study to be in the best interests of the participants.

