6.4. Post-Treatment Assessments

6.4.1. HBsAg Loss and Seroconversion Subjects

Subjects in Part A (renally impaired) who discontinue study drug due to HBsAg loss with confirmed seroconversion to anti-HBs on or after the Week 24 visit, will be followed off treatment every 4 weeks for 12 weeks and then per the original study visit schedule through Week 96/ED (excluding drug dispensation and accountability). Discontinuation of study drug for subjects experiencing HBsAg loss with confirmed seroconversion, who have known bridging fibrosis or compensated cirrhosis, should be considered on a case by case basis.

Subjects with moderate or severe hepatic impairment (Part B) who experience HBsAg loss and seroconversion to anti-HBs should not discontinue study drug.

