6.4.2. All Other Subjects Who Discontinue Study Drug

Subjects in Part A (renally impaired) who have received at least one dose of study drug and permanently discontinue study drug for reasons other than HBsAg loss with confirmed seroconversion to anti-HBs will be followed every 4 weeks for 24 weeks off treatment or up to initiation of appropriate, alternative HBV therapy, whichever occurs first. Use of appropriate, alternative HBV therapy is strongly encouraged.

For subjects in Part B (hepatic impairment) who permanently discontinue study drug, immediate initiation of appropriate, alternative HBV therapy is strongly recommended.

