6.4.3. Treatment-Free Follow Up Visit Assessments (Part A Subjects)

- Symptom directed physical exam
- Body weight
- Vital signs: blood pressure, pulse, respiration rate, and temperature
- Review concomitant medications
- Review adverse events

- Blood sample for serum chemistry and liver function tests, hematology, plasma HBV DNA levels, serum HBsAg (quantitative), HBV serology (qualitative HBsAg and HBeAg), eGFR_{CG}, and serum for storage
- Urine for urinalysis

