6.5. Early Discontinuation (ED)/Unscheduled Visit

A subject should attend an unscheduled visit if requested by the sponsor or the investigator.

The assessments at the unscheduled visits are at the investigator's discretion. At all unscheduled visits initiated for the purpose of confirming virologic rebound a serum blood sample for resistance testing must be collected.

If a subject discontinues study dosing (for example, as a result of an AE), every attempt should be made to keep the subject in the study and continue to perform the required study-related follow-up and procedures (see Section 6.6, Criteria for Discontinuation of Study Treatment). If this is not possible or acceptable to the subject or investigator, the subject may be withdrawn from the study.

The ED Visit should be performed within 72 hours (i.e., visit window is + 3 days) of the last study drug dose.

- Complete physical exam with vital signs (blood pressure, pulse, respiration rate and temperature) and body weight
- ECG (subjects must rest quietly in the supine position for a minimum of 5 minutes prior to the recording)
- DXA scan of spine and hip to be performed within \pm 14 days of the expected visit date and is done only if not done within the past 12 weeks of the ED visit
- Review concomitant medications
- Review adverse events
- Fasting blood sample for serum bone biomarkers and metabolic assessment (glucose and lipid panel [total cholesterol, HDL, direct LDL, and triglycerides]) – no food or drinks, except water, at least 8 hours prior to blood collection (only collected if not done in the last 12 weeks)
- Fasting urine sample for renal biomarkers for all subjects except for Part A, Cohort 2 (ESRD subjects on HD) – no food or drinks, except water, at least 8 hours prior to blood collection(only collected if not done in the last 12 weeks)

- Blood sample for serum chemistry and liver function tests (including PT/INR), hematology, plasma HBV DNA level, serum HBsAg (quantitative), HBV serology (qualitative HBsAg and HBeAg), eGFR_{CG}, virology (resistance surveillance), sparse plasma PK (all subjects except Part A, Cohort 2 [ESRD subjects on HD]), and serum and plasma for storage
- Blood sample for Fibrotest[®]
- CPT ([Appendix 7] Assessment requires: total bilirubin, albumin, PT/INR, Ascites assessment, and Hepatic encephalopathy assessment) for Part B subjects (hepatic impairment) only

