6.6. Criteria for Discontinuation of Study Treatment

Study medication may be discontinued in the following instances:

- Intercurrent illness that would, in the judgment of the investigator, affect assessments of clinical status to a significant degree. Following resolution of intercurrent illness, the subject may resume study dosing at the discretion of the investigator.
- Unacceptable toxicity, as defined in the toxicity management section of the protocol, or toxicity that, in the judgment of the investigator, compromises the ability to continue study-specific procedures or is considered to not be in the subject's best interest
- Therapeutic failure
- Part A (renally impaired) subjects only - HBsAg loss with seroconversion to anti-HBs. These subjects should discontinue study drug within 3-6 months following confirmation of seroconversion to anti-HBs. Subjects with HBsAg loss with confirmed seroconversion before Week 24 are not permitted to discontinue study drug prior to the Week 24 visit.
- Discontinuation of study drug for subject experiencing HBsAg-loss with confirmed seroconversion to anti-HBs, who have known bridging fibrosis or cirrhosis, should be considered on a case by case basis

- Any subject with $eGFR_{CG} < 15$ ml/min who does not initiate hemodialysis or initiates other forms of renal support (e.g. peritoneal dialysis) will be required to discontinue study treatment
- Subject request to discontinue for any reason
- Subject noncompliance
- Pregnancy during the study; refer to [Appendix 5](#)
- Discontinuation of the study at the request of Gilead, a regulatory agency or an institutional review board or independent ethics committee (IRB/IEC)

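### The SAP rule for a partly missing last-dose date has no upper limit, so for a Part A subject seen off drug it can place the last dose after the recorded month

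*SAP*

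**What the plan says.** SAP Section 3 treats two cases. A completely missing last-dose date goes to Section 3.8.1 of the base SAP, which is not among the documents. A partly missing date is handled in Section 3 itself. The candidates are the non-missing drug start and end dates plus every date of clinic attendance or laboratory sampling; the latest of these "will be used to impute the last dose date if the imputed month/year is no earlier than the partial last dose month/year". No other condition is stated, and no value is given for the case where this one fails.

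The protocol schedules off-drug visits for Part A only:

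- Subjects who stop for reasons other than HBsAg seroconversion, early or after 96 weeks, "will be followed every 4 weeks for 24 weeks off treatment" (Section 3.1), or "up to initiation of appropriate, alternative HBV therapy, whichever occurs first" (Section 6.4.2).
- Each such visit is a clinic date and a laboratory date. Section 6.4.3 lists "Blood sample for serum chemistry and liver function tests, hematology, plasma HBV DNA levels" among its assessments.
- Seroconverters who stop are seen every 4 weeks for 12 weeks and then "per the original study visit schedule through Week 96/ED (excluding drug dispensation and accountability" (Section 6.4.1). On timing, Section 6.6 says: "Subjects with HBsAg loss with confirmed seroconversion before Week 24 are not permitted to discontinue study drug prior to the Week 24 visit".

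Protocol Section 8.6.4 ends the treatment-emergent window at the last dose. Section 7.3 collects adverse events until 30 days after the last dose and serious adverse events through the whole post-treatment follow-up.

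**The concern.** A partial date usually still carries a known month and year. An imputation should fill in the missing day and leave the known part alone. This rule does that at the lower end only. If the subject has any visit after the recorded month, the rule discards the recorded month and takes the visit date.

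In Part A such visits are part of the schedule, for subjects who complete 96 weeks as well as for early stoppers. What is at stake is the attribution of safety events. Events that began after the drug was stopped, including a post-treatment hepatitis exacerbation that qualifies as serious, would be tabulated as arising on TAF. Protocol Section 8.2 reports by cohort, and Cohort 2 is small enough for one subject to be visible in a percentage.

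**Working it through.** The plan gives no figure for the imputation error, so there is none to reproduce. The sizes below follow from the protocol's visit schedule.

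**1. Stop for a reason other than seroconversion.** Visits every 4 weeks for 24 weeks: 24 / 4 = 6 visits. After *k* visits the imputed date is 28 × *k* days late: 28 days for one visit, 56 for two, 6 × 28 = 168 for all six.

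Example: true last dose 15 March 2019, recorded as March 2019, six visits attended. The latest date is 15 March + 168 days = 30 August 2019. August is not earlier than March, so the rule accepts it.

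**2. Does one visit already leave the recorded month?** A date 28 days later stays in the same month only for stops on days 1 to 3 of a 31-day month, days 1 to 2 of a 30-day month, or 1 February of a leap year. Over 2018 to 2021 that is 28 × 3 + 16 × 2 + 1 = 117 of 1461 days. The other 1344 / 1461 = 92.0% move into a later month.

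**3. Beyond the schedule.** Unscheduled visits (Protocol Section 6.5) can add later dates. Exacerbation follow-up (Section 7.5.5.2) may last up to 6 months from the event. If the event is first seen at off-drug Week 24, the error reaches 168 + 183 = 351 days.

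**4. Seroconverter followed to Week 96.** Week 96 is day 672.

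| Stop | Days late |
|---|---|
| Week 24 visit (earliest permitted) | (96 − 24) × 7 = 504 |
| 91 days after confirmation at Week 12 | 672 − (84 + 91) = 497 |
| 91 days after confirmation at Week 24 | 672 − (168 + 91) = 413 |
| Week 48 | (96 − 48) × 7 = 336 |
| Week 72 | (96 − 72) × 7 = 168 |

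The second and third rows read the 3-6 month period in Section 6.6 as including a minimum wait of 3 months. On frequency, the Phase 3 background in Section 1.2.3 says: "Three of the 4 subjects in the TAF group and none in the TDF group also experienced HBsAg seroconversion at Week 48". With 285 + 581 = 866 TAF subjects, that is 3 / 866 = 0.35%. Applied to 90 Part A subjects it gives about 0.3. This is only a rough guide, because the population differs and Week 48 is half of this study's treatment period.

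**5. Events moved into the treatment-emergent window.** Adverse events are collected for 30 days off drug, so the days relabelled are min(30, 28 × *k*): 28 for one visit, 30 for two or more. Serious adverse events are collected throughout follow-up, so their window grows by the full error.

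**6. Effect on an incidence, per affected subject.** At most 1 / 90 = 1.1 percentage points in Part A, and 1 / 18 = 5.6 to 1 / 16 = 6.3 points in Cohort 2. It is zero if the subject already has an on-treatment event in that category.

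**The case against.** The strongest reply is that no effect on results has been shown. Harm needs four things together: a partial date, a Part A subject, at least one off-drug visit, and a new event after the true last dose. Protocol Section 9.1.5 requires source records to hold the drug end date, and Section 9.1.6 describes queries on discrepancies. Alternative therapy ends follow-up and is encouraged. All of this stands, and it is why the point is minor.

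The supplied SAP text also supplements a base SAP that cannot be checked, and an on-treatment restriction or a fallback might sit there. That stands as a caveat. It does not rescue the rule as written, because Section 3 sends only completely missing dates to Section 3.8.1 and states the partial-date rule without pointing to any other restriction.

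The incidence shift is often nil for broad categories. In the Phase 3 studies 70.2% of TAF subjects had some adverse event (Protocol Table 1-5), and events leading to discontinuation are treatment-emergent in any case under Section 8.6.4.

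A reader might infer more than the documents support:

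- That 504 days is a typical error. It needs a seroconverter who stops at the earliest permitted visit and stays to Week 96.
- That 168 days is a maximum. It is the scheduled length only.
- That exposure and laboratory summaries are distorted as well. Protocol Sections 8.6.3 and 8.6.5 do not say that they use the imputed date.
- That the primary results are at risk. Those endpoints are at Week 24, and virologic response there does not depend on the last-dose date.

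**Conclusion.** The point holds, with low severity. As written, SAP Section 3 can override a recorded month and date the last dose to an off-drug visit. For a Part A subject with a partial date, the error is 28 days after one follow-up visit and 168 days after the full schedule. It can be longer with unscheduled or exacerbation visits, and rarely about 400 to 504 days for an early seroconverter followed to Week 96. The demonstrable consequence is that off-drug adverse events and serious adverse events are counted as treatment-emergent. This bears mainly on the Week 48 and Week 96 safety summaries.

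Part B has no scheduled off-drug visits and is essentially outside the problem. The conclusion assumes that the base SAP does not restrict the candidate dates. The number of partial dates is not given and is assumed small, so the documents do not support a claim that any reported rate would change materially.

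**What to change.** In SAP Section 3:

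1. When month and year are recorded, cap the imputed date at the last day of that month. If the latest candidate date is earlier than that month, use a pre-stated day within it, such as the 15th.
2. When only the year is recorded, cap at 31 December of that year, and state a fallback if no candidate date reaches that year.
3. Exclude treatment-free follow-up visits from the candidate dates. For subjects who stop after seroconversion, set the cut at the last visit with study drug dispensation or accountability. Their ED visit can fall long after the last dose, so it should not be used. For other early stoppers, use the ED visit held at drug discontinuation, which "should be performed within 72 hours (i.e., visit window is + 3 days) of the last study drug dose" (Protocol Section 6.5). For completers the Week 96 visit serves.

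The cost is a few lines of SAP text and a date condition in the code, with no new data. When the month is known, the residual error is at most 30 days (the 1st against the 31st), or 16 days under a 15th-of-month fallback. It is at most 3 days late when an on-time ED visit is the latest remaining date. Year-only dates can keep a larger error, up to 364 days (365 in a leap year) under the cap alone.

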4. SERUM CREATININE CORRECTION

A positive shift in serum creatinine values was observed due to a lot calibration change on 01 July, 2018, occurring across Covance laboratory sites worldwide. A correction was therefore applied to records on or after 01 July, 2018 to serum creatinine, following the regression equation specified in Table 4-1. The corrected serum creatinine values will be used for the analyses of serum creatinine, serum creatinine toxicity, eGFR estimated by the Cockcroft Gault formula, eGFR by the CKD-EPI method and other relevant parameters.

The corrected values must be in the same unit as the original values after going through the regression formula in Table 4-1.

- If the unit of serum creatinine is “μmol/L”, then use the formula directly.
- If the unit of serum creatinine is “mg/dL”, the values should be converted to “μmol/L” before using the formula.

After the correction, unit of serum creatinine should be converted back to “mg/dL” for summary and comparison purpose.

Table 4-1. Method of Serum Creatinine Correction

Regional Lab Center	Accession Number ^a	Regular Regression for Serum Creatinine (μmol/L) ^{b,c}
Indianapolis	starts with 65	$Y=1.002 \times X+1.77$
Geneva	starts with 62 or 63	$Y=1.025 \times X+2.62$
Shanghai	starts with 67	$Y=0.971 \times X+5.42$
Singapore	starts with 64 or 66	$Y=1.009 \times X-1.42$
Japan	start with 68	$Y=1.033 \times X+7.25$

a Accession numbers specified which regional lab center tested the sample. For example, samples with accession number starting with 65 were tested in Indianapolis Auto Chemistry Center.

b X and Y are the serum creatinine values from previous lot before 01 July, 2018 and serum creatinine values from new lot on or after 01 July, 2018, respectively.

c The serum creatinine correction is based on the unit of umol/L. The unit should be converted to mg/dL for summary purposes.

